## Response Measures

[figure not shown]
### *Efficacy:*

#### **Primary:**

- Change from baseline in number of episodes of urinary incontinence at Week 12 as recorded by the patient in the 3-day bladder diary.

#### **Secondary:**

- Proportion of patients who achieve 100% reduction in urinary incontinence episodes (complete continence) from baseline (ie, baseline prior to Treatment 1)
- Change from baseline in daily average number of micturition episodes
- Change from baseline in daily average number of urgency episodes
- Change from baseline in daily average number of nocturia episodes
- Proportion of patients who have a positive treatment response on the TBS (score of either 1 or 2, representing 'greatly improved' or 'improved', respectively).

### *Safety:*

- Adverse events and serious adverse events (SAEs)
- Physical examination
- Vital signs
- PVR urine volume (by bladder scan or ultrasound)
- Pregnancy test for women of childbearing potential (at screening, before study treatment(s) and at study exit)
- Urine dipstick reagent strip test
- Central laboratory urine analysis
- Urine culture and sensitivity
- Concomitant medications
- Concurrent procedures (including catheterization with associated frequency and reason for catheterization).

**General Statistical Methods and Types of Analyses:** Efficacy endpoints will be analyzed using the modified intent-to-treat (mITT) Population. The primary efficacy endpoint is the change from baseline at Week 12 in the daily average number of episodes of urinary incontinence, as recorded in the 3-day bladder diary.

Comparison of BOTOX 100 U and placebo at Week 12 for the primary efficacy endpoint and other continuous endpoints will be performed using analysis of covariance with treatment as a factor, and baseline value and the number of urgency incontinence episodes reported at baseline ( $\leq 9$  or  $> 9$  daily episodes, over the 3-day bladder diary at baseline) as covariates. The 95% confidence interval (CI) for the least squares (LS) mean difference between BOTOX 100 U and placebo will be constructed.

Comparison of BOTOX 100 U and placebo at Week 12 for the proportion of patients with 100% reduction in urinary incontinence episodes from baseline and other categorical endpoints will be analyzed using Cochran Mantel-Haenszel (CMH) method with the number of urgency incontinence episodes reported at baseline ( $\leq 9$  or  $> 9$  daily episodes, over the 3-day bladder diary at baseline) as another categorical factor. The 95% CI for the odds ratio of BOTOX 100 U over placebo will be constructed.

Safety endpoints (including adverse events, laboratory urine data, vital signs, and PVR urine volume) will be summarized descriptively by treatment based on the Safety Population.

[figure not shown]
*Sample Size Calculation:*

[figure not shown]
The assumptions used for sample size calculation are from the Phase III pivotal studies (191622-095 and 191622-520) results.

Assuming a mean and standard deviation of change from baseline at Week 12 in the number of urinary incontinence episodes are  $-2.8 (\pm 3.45)$  and  $-0.95 (\pm 2.9)$  for BOTOX 100 U and placebo, respectively, this study requires 102 patients (68 BOTOX patients and 34 placebo patients) to provide 80% power for detecting a significant difference of the primary efficacy endpoint (change from baseline in number of urinary incontinence episodes at Week 12) at a significance level (alpha) of 5% using a 2-sided z-test at the end-of-study analysis.

With 10% dropout rate, the sample size required for the patients to be randomized in the study will be approximately 114 patients.

## 1. Background and Clinical Rationale

### *Overactive Bladder and Urinary Incontinence*

Overactive bladder (OAB) syndrome is a symptom-based diagnosis and is defined as urgency, with or without urgency incontinence, usually with frequency and nocturia (Abrams et al, 2002). These symptoms are a consequence of the bladder's inability to effectively store urine due to an underlying dysfunction in the coordinated mechanisms that provide controlled storage and voiding of urine. However, in the absence of a known neurological insult or pathophysiological cause, the reason for dysfunction is unknown in the majority of cases resulting in the condition known as idiopathic OAB.

### *Epidemiology and Impact of Overactive Bladder*

OAB is a prevalent disorder that is reported to affect between 12% and 17% of the general population in North America and Europe (Milsom et al, 2001; Stewart et al, 2003; Irwin et al, 2006; Herschorn et al, 2008), with a similar prevalence also being reported in Asia and South America (Homma et al, 2005; Yu et al, 2006; Teloken et al, 2006). Overall, approximately one third of OAB patients have OAB with urinary urgency incontinence, or 'wet OAB' (Irwin et al, 2006). Both OAB and 'wet' OAB increase with advancing age, and the rate of increase 'wet' OAB with age is greater in women than men (Milsom et al, 2001; Tubaro, 2004). Urinary incontinence carries a considerable social stigma and many sufferers are unable to continue with their activities of daily living or are unable to continue with employment.

### *Currently Available Therapy*

Therapy for OAB focuses on the symptomatic relief of patient symptoms. Treatment for OAB typically begins with bladder training, pelvic floor muscle training, and lifestyle advice. Pharmacological therapy is generally limited to the use of anticholinergic agents and recently beta-3 agonists. However, the utility of oral medicines can be limited by inadequate efficacy or intolerable side effects, such as dry mouth, constipation, or cognitive deficits (Chapple et al, 2008). This often results in poor treatment compliance by the patient and cessation of treatment by physicians (Lawrence et al, 2000; Kreder et al, 2002). Analysis of a database containing information from 29,369 women prescribed anticholinergics for lower urinary tract symptoms in the United Kingdom reported discontinuation rates of 59% by 6 months (Gopal et al, 2008). The overall 'switch rate' to another anticholinergic was low at 15%; however, in a subset of patients there was a high switch rate (approximately 60%),

which the authors suggested represents patients with severe symptoms who are still willing to try new medications in order to achieve relief from their condition.

There are few second-line treatment options available for patients with OAB who do not have sufficient benefit with oral therapies. Surgical implantation of sacral nerve stimulation/neuromodulation systems is an option; however, the nature of this intervention means that reoperation is required due to the limited longevity of the neurostimulator ([Starkman et al, 2010](#)). In addition to battery wear or lack of effect, reoperation or explanation can also occur for various reasons such as lead migration, infection, or pain at the stimulator site ([Hijaz et al, 2006](#); [Starkman et al, 2010](#)). Peripheral tibial nerve stimulation (PTNS) for OAB treatment involves the percutaneous placement of a needle electrode in the medial malleolus of the ankle which then delivers an electrical stimulation of the posterior tibial nerve. At least weekly sessions of 30 minutes are required in the initial months, as well as subsequent maintenance sessions ([Peters et al, 2010](#); [MacDiarmid et al, 2010](#)). The durability of response is uncertain following PTNS and there is limited controlled data with this type of device in the OAB population ([Starkman et al, 2010](#)).

For patients with intractable symptoms, the only remaining option is major reconstructive surgery such as augmentation cystoplasty with the aim of increasing the capacity of the bladder. In addition to the risk of a major surgical procedure, complications such as metabolic disorders and chronic retention are common, and these procedures do not guarantee continence.

The recent approval of BOTOX (onabotulinumtoxinA) in adults with OAB who have had an inadequate response to an anticholinergic has added an important second line prescription treatment option for this population .

#### *BOTOX Development Program*

The Allergan clinical development program for BOTOX in patients with OAB and urinary incontinence was initiated with a phase II study (191622-077) that evaluated a range of BOTOX doses (50, 100, 150, 200, and 300 U) versus placebo. A total of 313 patients were enrolled and the study showed improvements in OAB symptoms and urodynamic parameters at doses of 100 U and above. This was also reflected in consistent improvements in health-related quality of life (HRQOL) at doses of 100 U and above. A dose-dependent safety profile was identified with respect to adverse events of urinary retention and urinary tract infection (UTI), as well as in post-void residual (PVR) urine volume and use of clean

intermittent catheterization (CIC). The dose of 100 U was evaluated as providing the appropriate benefit/risk balance in the target population.

A phase III program was subsequently initiated that included 2 identical double-blind, randomized, pivotal phase III studies (Studies 191622-095 [Nitti et al 2013](#); and 191622-520 [Chapple et al. 2013](#)), both of which evaluated a dose of BOTOX 100 U compared to placebo. A total of 1105 patients were enrolled in the pivotal studies. Both of these phase III pivotal studies assessed patients for at least 24 weeks, with the opportunity for retreatment with BOTOX 100 U if prespecified retreatment criteria were met from 12 weeks onwards. The co-primary measures in both studies were the number of episodes of urinary incontinence and the proportion of responders on the Treatment Benefit Scale (TBS), defined as patients who rated their perception of response to treatment as either ‘greatly improved’ or ‘improved’ compared to baseline. The primary timepoint was Week 12 following the first study treatment.

Both pivotal phase III studies, 191622-095 and 191622-520, achieved a statistically significant and clinically relevant treatment effect of BOTOX 100 U, and results were consistent between the 2 studies. The co-primary efficacy endpoints were met in both studies ( $p < 0.001$ ), with clinically meaningful reductions from baseline in urinary incontinence and clear patient perception of improvement in their condition using the TBS. Furthermore, all secondary endpoints were met in both studies, which included OAB symptoms and HRQOL parameters. Specifically, BOTOX 100 U attenuated all OAB symptoms; thus a significant treatment effect was observed for urinary incontinence, micturition frequency, urgency, and nocturia. The improved ability of the bladder to store urine was reflected in significant increases in volume voided per micturition. Similarly, the secondary endpoints of change from baseline in the Incontinence Quality of Life total summary score and the change from baseline in the 2 multi-item King’s Health Questionnaire (KHQ) domain scores ‘Role Limitations’ and ‘Social Limitations’ at Week 12 were also met ( $p < 0.001$ ).

In terms of safety, adverse events that were higher following BOTOX treatment compared to placebo were primarily limited to local adverse events related to the urinary tract, in particular UTI, bacteriuria, dysuria, and urinary retention. A dose-dependent increase in PVR urine volume was observed post treatment, and a proportion of those patients initiated CIC. However, the proportion of patients with a change from baseline PVR urine volume  $\geq 200$  mL at any time during treatment was low (less than 9% in both studies), and correspondingly, the proportion of patients who initiated CIC was also low (6.5%).

Patients who were enrolled in the pivotal phase III studies had the opportunity of enrolling into a long-term follow-up study, 191622-096. This study has been completed (N=839), and patients will participate in the follow-up study for up to an additional 3 years and receive only active treatment (on fulfillment of Qualification and Day of Treatment Criteria). The final analysis of this extension study demonstrated a consistent efficacy and safety profile over repeated BOTOX treatments.

As the use of BOTOX has evolved over the past few years after marketing approval, more data have emerged on the efficacy and risks of BOTOX use. The established scientific data describing the enervation and contractility of the bladder, coupled with better understanding of the mechanism of action of BOTOX on the sensory enervation has led to a hypothesis that is the basis for this study. Based on these emerging data as well as many unpublished anecdotal reports, injecting BOTOX into the lower portion of the bladder and trigone may have a more profound effect on the afferent portion of the OAB complex without markedly affecting the normal functions of the bladder musculature during normal voiding. This hypothesis postulates that by altering the injection paradigm of BOTOX in OAB patients, similar efficacy to that of the current paradigm could be achieved while reducing the risk of partial urinary retention requiring CIC in those patients.

The purpose of this study is to test the above hypothesis by evaluating the efficacy and safety of an alternative injection paradigm for BOTOX 100 U with respect to occurrence of urinary incontinence episodes in patients with OAB and its impact on their quality of life (QOL).

## **2. Study Objectives and Clinical Hypotheses**

### **2.1 Study Objectives**

The primary objective of this study is to evaluate the efficacy and safety of BOTOX 100 U (onabotulinumtoxinA), compared to placebo, when injected into the bladder using an alternative injection paradigm (2 trigonal and 8 peri-trigonal injections) in reducing the number of daily urinary incontinence episodes in patients with OAB and urinary incontinence whose symptoms have not been adequately managed with an anticholinergic.

The secondary objectives of this study are to evaluate the QOL impact, duration of treatment effect, early onset of treatment effect, and safety of BOTOX (100 U) in patients with OAB and urinary incontinence whose symptoms have not been adequately managed with an anticholinergic.

## 2.2 Clinical Hypotheses

BOTOX 100 U is more effective compared to placebo, when injected into the bladder using the alternative paradigm (2 trigonal and 8 peri-trigonal injections), in reducing the number of daily urinary incontinence episodes from baseline at Week 12.

BOTOX 100 U has an acceptable/better safety profile, including the risk of incomplete bladder emptying and need for clean intermittent catheterization (CIC), when administered as 10 injections into the lower part of the bladder (2 trigonal and 8 peri-trigonal) of patients with OAB with urinary incontinence.

BOTOX 100U administered into 10 injection sites limited to the lower portion of the bladder (alternative paradigm) rather than 20 sites in the posterior wall is effective in achieving efficacy in patients with OAB while reducing the risk of incomplete bladder emptying in those patients.

BOTOX 100 U, administered using an alternative injection paradigm, is effective for longer duration than placebo as assessed by the difference between treatment groups in the time to qualification for second treatment (qualification for Treatment 2 criteria provided in [Section 5.10.1](#) Request/Qualification for Treatment 2) during the 30 weeks of follow-up after the first treatment injection.

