## 5.6 Treatment Regimen and Dosing

### 5.6.1 Study Treatments

BOTOX

#### Study Treatment 1

All eligible patients who meet inclusion/exclusion criteria and are enrolled into the study will receive a double-blind treatment of either BOTOX 100 U or placebo for their first study treatment.

The first treatment will be administered after randomization on Day 1 at the investigational site. All Day of Treatment Criteria must be fulfilled prior to treatment administration (see [Section 5.9.1 Day of Treatment 1 Criteria](#)).

#### Study Treatment 2

All patients can request and potentially qualify for a second treatment, and if the qualification criteria are met (Qualification for Treatment 2 Criteria provided in [Section 5.10.1 Request/Qualification for Treatment 2](#)) they will receive BOTOX 100 U for their second treatment.

Administration of Treatment 2 should occur within 28 days of the qualification for Treatment 2 visit. Patients must fulfill the ‘Day of Treatment 2 Criteria’ prior to Treatment 2 administration (see [Section 5.10.2 Day of Treatment 2 Criteria](#)). Treatment 2 must not be administered before 12 weeks after Treatment 1.

The reason(s) for the patient requesting retreatment will be collected at each visit in which the request is made, regardless of whether the patient qualifies for Treatment 2 at that visit or not.

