## **5.10        Retreatment**

### **5.10.1      Request/Qualification for Treatment 2**

Patients may request Treatment 2 at the Week 12 clinic visit or any time thereafter up to Week 30. A qualification visit will be added to the patient's schedule if the request for retreatment is made outside the regular prescheduled visits. A clinic visit (prescheduled or unscheduled) at which the patient is assessed after making a request for a second treatment will then become a Qualification for Treatment 2 visit, and is no longer considered the post-treatment visit, and the appropriate eCRFs should be completed. Treatment 2 should occur within 28 days of qualification and no later than Week 34 (+/-7 days). The patient must meet all qualification criteria before Treatment 2 can occur.

The 'Qualification for Treatment 2 Criteria' are:

- Patient must initiate request for Treatment 2
- Patient experiences  $\geq 2$  episodes of urinary urgency incontinence, with no more than 1 urgency incontinence-free day, as determined by the 3 consecutive days of bladder diary completion in the week prior to the qualification for Treatment 2 visit (ie, Week 12, 24 or 30 post Treatment 1 or an additional visit, depending on the timing of the retreatment request).
- PVR urine volume must be  $< 200$  mL.
- Investigator deems that Treatment 2 is medically appropriate and no condition or situation exists which, in the investigator's opinion, puts the patient at significant risk from receiving a second treatment.
- A minimum of 12 weeks must have elapsed since Treatment 1.

Once a patient has met the 'Qualification for Treatment 2 Criteria', the patient is considered qualified for Treatment 2 and may proceed with the treatment visit (see [Section 5.10.2](#)). The Treatment 2 visit may occur on the same day of qualification or may be scheduled on another day if the Treatment 2 criteria are not met. If the Treatment 2 visit is rescheduled, visit procedures for which the patient has already been qualified do not need to be repeated.

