### **6.3.4        Bladder Diary**

All patients will be provided a e-Diary in which to record electronically 3 consecutive days of required bladder diary information. Prior to receiving the e-Diary, patients will be instructed and trained on the use of the electronic diary and the data to be collected. Patients will be required to collect bladder diary data over 3 consecutive 24-hour periods during the week prior to scheduled clinic visits (for screening period only, the diary can be completed for 3 consecutive 24-hour periods at any time during the screening period). Patients must bring the e-Diary to each clinic visit. The electronic diary will capture the following information (terms used on the diary will be patient friendly):

- date and time of urinary episode
- episodes of micturition (toilet voids)
- episodes of urinary incontinence
- episodes of urgency
- episodes of nocturia (voids that awaken from normal sleep)
- start and stop date of CIC
- volume of each void measured over one 24-hour period during the 3-day bladder diary collection period. This will be used to calculate the volume voided per voiding episode (see [Section 6.3.5 Total Volume Voided](#)).

More detailed instructions on the use of the e-Diary and completion of the electronic patient bladder diary will be provided to the patient.

The electronic diary data will also be used to satisfy eligibility requirements for study entry, as well as to qualify the patient for Treatment 2.

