### 7.3.2 Secondary Efficacy Analyses

The 5 secondary endpoints are listed in [Section 7.2.2](#).

The analysis of all secondary endpoints will be based on the mITT Population.

The first and the last secondary endpoints on the list are categorical variables, and they will be analyzed using a Cochran Mantel-Haenszel (CMH) test with the number of UUI episodes reported at baseline ( $\leq 9$  versus  $> 9$  daily episodes, during the 3-day bladder diary at baseline) as another categorical factor at each scheduled visit. Point estimate and the 95% CI for the odds ratio (BOTOX 100 U/placebo) will be calculated.

The second to the fourth secondary endpoints on the list are continuous variables. Each of the 3 continuous endpoints will be analyzed at each scheduled visit using an ANCOVA model with treatment as a factor and baseline value corresponding to the given endpoint and the number of UUI episodes reported at baseline ( $\leq 9$  versus  $> 9$  daily episodes, during the 3-day bladder diary at baseline) as covariates. A 95% CI for the LS mean difference of a given endpoint between the 2 treatments will be calculated. A paired t-test will be performed to compare the baseline value to a post-treatment value at each visit for each endpoint.

between the 2 treatments will be constructed. A paired t-test will be performed for the comparison between baseline and a post-treatment value at each visit for each endpoint.

The categorical endpoints will be analyzed using a CMH test with the number of UUI episodes reported at baseline ( $\leq 9$  versus  $> 9$  daily episodes, during the 3-day bladder diary at baseline) as another categorical factor at each visit. Point estimate and 95% CI for the odds ratio will be calculated for each endpoint at each visit.

The time-to-first-event endpoint will be analyzed using the Kaplan-Meier procedure for median time-to-request of re-treatment event by days (and weeks). Between-group comparisons of the 2 treatments will be performed using the log-rank test. A 95% CI for the median time-to-request of re-treatment for each treatment will be calculated.

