## **8. Study Visit Schedule and Procedures**

Please see [Table 1](#) for a schematic of the schedule of visits and procedures and [Figure 1](#) for a flow diagram. Refer to [Section 6.3](#) for detailed information on study procedures, tests, equipment, and techniques.

The visit schedule is described below.

Also, the occurrence of adverse events and SAEs at any time after informed consent through the post-treatment exit visit will be monitored and recorded. Use of concomitant medications will be recorded during the screening period, treatment and post-treatment follow-up through the exit visit.

A series of horizontal black bars of varying lengths, likely representing data points or categories in a bar chart. The bars are arranged in a grid-like pattern across the page. The lengths of the bars vary significantly, with some being very short and others being very long, creating a visual representation of data distribution.

A series of 20 horizontal black bars of varying lengths, arranged vertically. The bars are of different widths, with some being very narrow and others very wide, creating a visual pattern of varying lengths.

Unscheduled visits will be performed if safety concerns arise, at the discretion of the investigator, as well as for qualification for Treatment 2 in the case of a patient's request for retreatment occurring outside the prescheduled visits. Additional examinations may be performed as necessary to ensure the safety and well being of patients during the study. Additional unscheduled visits will occur if a patient has a post-treatment PVR urine volume of  $\geq 200$  mL (for additional details see [Section 6.3.6](#) Full Bladder Volume and Post-void Residual Urine Volume).

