5.5.4 Analysis of Time to Request of Re-Treatment

The time-to-request of re-treatment between the two treatments will be analyzed using the log-rank test. Kaplan-Meier estimates of the time-to-request of re-treatment will be provided. A 95% CI for the median time-to-request of re-treatment for each treatment will be calculated.

6 Safety Analyses

All safety analyses will be conducted on the safety population. No inferential comparison between treatment groups will be performed for the safety analysis.

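### Protocol 2.2 states the duration hypothesis on time to qualification for Treatment 2, but the visible Kaplan-Meier and log-rank analyses use time to request

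*Protocol*

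**What the plan says.** Protocol 2.1 makes duration of effect a secondary objective. Protocol 2.2 turns it into a hypothesis "as assessed by the difference between treatment groups in the time to qualification for second treatment", refers to Section 5.10.1 for the criteria, and sets a window of 30 weeks after the first injection.

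The visible analysis text names another event. In protocol 7.3, after a redacted break that follows the secondary analyses, a single time-to-first-event endpoint is to be analysed by the "Kaplan-Meier procedure for median time-to-request of re-treatment event by days (and weeks", with a log-rank comparison and a confidence interval for the median. SAP 5.5.4 repeats this: "The time-to-request of re-treatment between the two treatments will be analyzed using the log-rank test". SAP 8 declares no change from the protocol-specified analysis.

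Section 5.10.1 lists five qualification criteria: the patient's own request, urgency incontinence on the diary, PVR below 200 mL, the investigator's judgement, and at least 12 weeks since Treatment 1. Section 5.6.1 collects the reason for each request "regardless of whether the patient qualifies for Treatment 2 at that visit or not". Section 10.4.1 lists the request date or dates and the qualification date as separate source items.

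**The concern.** The hypothesis and its test should concern the same event. A request records what the patient wants. Qualification adds diary-confirmed symptoms, a residual-volume limit and the investigator's opinion. The two can give different event counts, different medians and a different log-rank result.

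Two consequences follow. A log-rank result on requests would be reported against a hypothesis about qualification. And while both wordings stand, the duration claim could be attached to either event after the results are seen. Protocol 7.6 and SAP 7 send topline results to sponsor team members and co-authors before the final database lock, so it matters when the choice is made.

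**Working it through.** The duration endpoint has no visible planning figure to reproduce: no hazard ratio, event count or power is given for it. The only sample-size figure, in protocol 7.5, is for the primary endpoint. It reproduces closely: (1.96 + 0.84)² × (3.45²/2 + 2.9²) / 1.85² = 32.9, so 33 placebo and 66 BOTOX patients, 99 in all against 102 stated. Power at 68/34 is Φ(1.85/√(3.45²/68 + 2.9²/34) − 1.96) = 81% against 80% stated. Re-treatment events do not enter that calculation, so it is unaffected.

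The check itself compares text. Taking each document as visibly worded, and the first request as the event in the analysis:

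| Patient's course | Hypothesis (protocol 2.2) | Analysis (protocol 7.3, SAP 5.5.4) |
|---|---|---|
| Never requests | No event | No event |
| Requests and qualifies at one visit | Event | Event, same date |
| Requests between visits, qualifies at an added visit | Event at the added visit | Event at the earlier request |
| Requests, fails a criterion, qualifies later | Event at the later visit | Event at the first request |
| Requests, never qualifies | No event | Event |

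The protocol provides for each course in which the columns differ.

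1. *Request without qualification.* Section 5.6.1 plans for it, and four criteria besides the request have to be met.
2. *Request between visits.* Section 5.10.1 adds a visit "if the request for retreatment is made outside the regular prescheduled visits", and Section 8 allows unscheduled visits for a "request for retreatment occurring outside the prescheduled visits". Qualification there is "as determined by the 3 consecutive days of bladder diary completion in the week prior to the qualification for Treatment 2 visit". The routine diary rule covers only the run-up to planned visits: "Patients will be required to collect bladder diary data over 3 consecutive 24-hour periods during the week prior to scheduled clinic visits". A patient without a current diary would need about three more days.
3. *Failure, then later qualification.* On the nominal visits named in 5.10.1, the gap could reach (24 − 12) × 7 = 84 days from Week 12 to Week 24, or (30 − 24) × 7 = 42 days from Week 24 to Week 30. An unscheduled visit in between would shorten it. These are possible gaps for one patient, not estimates for the trial.

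The visit label does not settle the matter. Under 5.10.1 the visit at which a requester is assessed becomes the qualification visit whatever the outcome; the patient counts as qualified only once the criteria are met.

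The trial-level effect cannot be computed. It depends on how often requesters fail or ask off-schedule, and on whether this differs between arms. The documents give neither.

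**The case against.** The strongest reply is that the deciding text may be hidden. The protocol's contents list has a blacked-out entry between 7.3.2 and 7.3.4, the amendment log refers to Sections 6.1.3, 7.2.3 and 7.3.3, and SAP 5.4 and 5.5.1 are not visible. A redacted section could define the event as the request that led to qualification, or list a time-to-qualification endpoint. This stands as a limit: the point covers visible wording only. It does not remove the point, because 2.2 and both visible analysis texts still name different events.

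Second, the events overlap. Request is itself a criterion, and a patient who asks and qualifies at one scheduled visit has one date for both. That is true, and it may describe most patients, but nothing visible says so.

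Third, the stakes are modest. Time to re-treatment is not among the five secondary variables, and duration is not a key hypothesis in the Protocol Summary. That also stands.

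Fourth, request may be the better event, since PVR and investigator judgement can delay qualification for reasons unrelated to loss of effect. This is a fair argument for rewording 2.2, not for leaving the texts in disagreement.

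A reader might also infer that the SAP departs from the protocol. It does not: the mismatch lies inside the protocol, and the SAP follows the protocol's analysis text.

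**Conclusion.** The point holds for the visible text. As written there, the log-rank test and the median describe time to request, whereas the hypothesis concerns time to qualification. It is worth correcting because duration is a stated secondary objective and one of the four hypotheses in 2.2. The primary endpoint, the five secondary variables and the sample size are unaffected.

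Three stronger readings are tempting but not supported:

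- *The duration comparison is biased toward one arm.* Section 1 reports PVR increases after treatment in earlier studies, so the PVR criterion could delay qualification on BOTOX. How often it would do so here, and what the other criteria would do in each arm, is not given.
- *The mismatch costs a known amount of power.* Any such figure needs assumed request rates and qualifying shares by arm, and its direction changes with those shares.
- *Event-date or censoring rules are missing.* They may be in redacted sections.

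The conclusion assumes only that the redacted text does not already reconcile the two events.

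**What to change.** Choose one of two changes.

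- **Test on qualification.** In SAP 5.5.4, and in the matching text of protocol 7.3, add a log-rank test and Kaplan-Meier estimates by arm of time from Treatment 1 to the first visit at which all Section 5.10.1 criteria are met. Name this as the test of the duration hypothesis in 2.2 and keep time to request as a supportive analysis.
- **Test on request.** If request is the intended event, reword 2.2 to say so and leave the analysis as it is.

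Either way, name one event as the test before final unblinding, and record the date of the change relative to release of the Week 12 topline. Follow any event-date or censoring rules already set in the redacted sections.

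The first option costs one further time-to-event analysis. Both dates are already required in source records by Section 10.4.1; the sponsor should confirm that both reach the analysis database. SAP 1 allows revisions before database hard lock. Its downsides are small: possibly fewer events, and delays from the PVR or investigator criterion that do not reflect loss of effect. The two analyses should therefore be read together. The second option costs one line. Neither alters any re-treatment criterion.
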